6 STUDY MONITORING

6.1 MONITORING

The investigator/institution will permit trial-related monitoring, audits, REB review and regulatory inspections(s), and will provide direct access to source data/documents as required.

The multicentre research coordinator will be responsible for the training of research staff and conducting monitoring visits in the anticipated 3 centers. Remote monitoring methods will be used. An initiation teleconference will be performed in each center before commencement of the trial. Monitoring at each center will be performed to ensure that patient safety, study procedures, and data collection are performed in accordance with the research protocol and GCP/ICH guidelines. The detailed monitoring plan can be found in the resource manual.

7.2 DATA AND SAFETY MONITORING BOARD

The DSMB will be comprised of clinicians and methodologists who are independent of the sponsor and study investigators but have experience with clinical trials and can be relied upon to exercise good judgment in weighing the potential risks and benefits to patients as data accumulate in the trial. The committee will review data on a regular basis for monitoring safety

of the patients exposed to the study medication. The DSMB will have an independent associated statistician who will receive study data from the central database and will remain independent of the trial management team.

7 PROTOCOL DEVIATIONS/VIOLATIONS

Study related procedures must be conducted in compliance with the protocol, amendments, regulations and guidelines, in order to ensure participant safety and data integrity. Any deviations from the protocol, or violations of the protocol, will be accurately documented, reported and reconciled.

7.1 PROTOCOL DEVIATIONS

Protocol deviations refer to incidents involving non-compliance with the protocol that are unlikely to have a significant impact on the participant's rights, safety or welfare, or on data integrity. Examples of deviations include: forgetting to complete a procedure at a specified visit (weight, missing lab value, etc.).

If a protocol deviation occurs the following procedures will be followed:

- The local investigator or delegate will document and explain any deviation from the approved protocol
- Deviations from the protocol must be reported in the study source document
- Deviations will be reviewed during monitoring visits.

7.2 PROTOCOL VIOLATIONS

Protocol violations refer to more serious incidents involving non-compliance with the protocol that may result in significant effect on the participant's rights, safety, or welfare or data integrity.

Protocol violations could result in the participant being excluded from the eligibility analysis and/or result in the participant being discontinued from the trial. Examples of violations include: non-compliance with inclusion/exclusion criteria and dosing administration.

If non-compliance is identified, the following procedures will be followed:

- All protocol deviations will be recorded in a log
- The site investigator or delegate will notify the coordinating centre in Ottawa as soon as possible after discovering the violation.
- The site investigator or delegate will document: the details and reason for the protocol violation. The documentation will also include an assessment by the site investigator with regards to the impact of the protocol deviation on the participant or trial data. Follow-up procedure and corrective action to prevent future violations will also be documented.
- Violations will be recorded in the study source document and on the protocol violation form

- All violations will be reported to the local research ethics board (according to local policies)
- All violations will be reported and reviewed by the Data and Safety Monitoring Board.

8 STATISTICS

8.1 STATISTICAL AND ANALYTIAL PLANS

8.1.1 ANALYSIS OF BASELINE CHARACTERISTICS

Descriptive statistics will be used to examine the baseline characteristics of excluded subjects and those in the experimental and standard of care arm. Standard deviations will be reported for all characteristics expressed as continuous variables. Medians and ranges will be presented for discrete data.

8.1.2 PILOT TRIAL PRIMARY ANALYSIS

The primary analysis will involve a simple estimate of the mean monthly recruitment rate per site along with the 95% confidence interval of the mean.

8.1.3 PILOT TRIAL SECONDARY ANALYSES

Proportions with 95% confidence intervals will be calculated using Wilson's score method for the following secondary analyses: 1) proportion of screened subjects who meet eligibility criteria, 2) proportion of eligible subjects who provide consent, 3) proportion of withdrawals/losses to follow-up among randomized subjects, 4) proportion of sites requiring >18 months to obtain all required approvals/contracts from time of delivery of all study documents, and 5) proportion of crossover between study arms. Reasons for non-consent will be collected and analyzed using qualitative thematic analysis.

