2. STUDY SYNOPSIS

Title: A pilot study assessing the feasibility of a randomized controlled trial investigating primary thromboprophylaxis with rivaroxaban in patients with malignancy and central venous catheters (CVC)

Short Title: The TRIM-Line

Protocol Version: 28Feb2018 Version 1.1

Principal Investigators: [name] and [name]

Sponsor: OHRI

Study Centres:

The Ottawa Hospital, General Campus, Ottawa, ON
QEII Health Sciences Centre, Halifax, Nova Scotia
University of Alberta Hospital, Edmonton, Alberta

Timeline: February 2019-September2019

Purpose of Pilot Trial

To determine the feasibility of conducting a multicentre randomized open label-controlled trial evaluating the use of prophylactic dose rivaroxaban to prevent CVC associated venous thromboembolism(VTE) among cancer patients.

Purpose of Full Trial

The purpose of the full trial is to determine the efficacy and safety of prophylactic dose rivaroxaban to prevent CVC associated VTE among cancer patients.

Pilot Trial Endpoints

The primary feasibility outcome for the pilot study is the number of participants recruited per centre per month. We will obtain baseline details of the patient's type, location and treatment of cancer, comorbidities and medications. Secondary feasibility outcomes of the pilot study will include, consent rates, loss to follow up, adherence to therapy defining 80% or greater medication taken as having good adherence to study drug, proportion of screened patients who meet eligibility criteria.

We will document reasons for non-consent in order to assist recruitment for the larger multicentre trial.

Full Trial Endpoints

For the full multicentre trial the outcomes would be as follows: primary outcome symptomatic, radiographically confirmed VTE. Secondary outcomes include major and clinically relevant non-major bleeding (CRNMB), CVC life span, premature CVC removal, CVC lumen occlusion, CVC associated infection and death.

Design

This is a pilot study to be conducted at 3 Canadian Centres. The Ottawa Hospital, QEII Health Science Centre and University of Alberta Hospital. It is an open label randomized controlled trial.

Consenting participants, meeting eligibility criteria will be randomized at the time of enrollment to one of two groups.

Rivaroxaban 10mg po daily x 90 days

OR

Observation

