4.3 TRIAL INTERVENTION

Eligible and consenting patients will receive rivaroxaban 10 mg tablets to be taken once daily, starting within 72 hours of CVC placement. Randomization will occur in a 1:1 ratio via a central web-based randomization system.

The study drug will be continued until the CVC is removed, until one of the study outcomes is achieved, or until the end of the follow-up (90 Days +/- 3 days). Study medication will be held if the platelet count is $50 \times 10^9/L$ or less, the CrCl falls below 30mL/min, the patient experiences bleeding or the patient is required for treatment of cancer to start on a medication or chemotherapy which has a major interaction with rivaroxaban. All patients will be followed for 90 days (+/-3 days), unless they die or withdraw permission for follow up. At the end of the trial, VTE prophylaxis will be left to the discretion of the local investigator.

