4.4 ELIGIBILITY

Inclusion and Exclusion Criteria

Inclusion criteria:

Patients 18 years of age or older with a new or existing diagnosis of cancer with a CVC inserted in the last 72 hours.

Exclusion criteria:

- 17) CVC in place for >72 hours
- 18) Patient requires anticoagulation for other indication
- 19) Concomitant use of dual antiplatelet therapy
- 20) Prior VTE
- 21) Major bleeding event in the last 6 weeks
- 22) Patient on concomitant medication with known interaction with rivaroxaban (eg. CYP3A4 inhibitor)
- 23) Pregnancy (documentation of use of effective contraception if sexually active or negative B- Hcg required) **
- 24) Known renal failure, based on Creatinine clearance <30 mL/min (Cockcroft-Gault) (in the previous 3 months)*
- 25) Documented severe liver disease (eg. acute clinical hepatitis, chronic active hepatitis, cirrhosis or ALT >3ULN) (in the previous 3 months)*
- 26) Known thrombocytopenia < 50x 10⁹/L (in the previous 3 months)*
- 27) Allergy to rivaroxaban
- 28) Life expectancy <6 months
- 29) History of condition at increased bleeding risk including, but not limited to:
 - g) Major surgical procedure or trauma within 30 days before the randomization visit
 - h) Clinically significant gastrointestinal bleeding within 6 months before the randomization visit
 - i) History of intracranial, intraocular, spinal, or atraumatic intra-articular bleeding
 - j) Chronic hemorrhagic disorder
 - k) Known intracranial neoplasm, arteriovenous malformation, or aneurysm
 - l) Sustained uncontrolled hypertension: systolic blood pressure ≥180 mmHg or diastolic blood pressure ≥100 mmHg
- 30) Primary malignancy diagnosis of basal cell or squamous cell carcinoma of the skin or acute leukemia or myelodysplastic syndrome
- 31) Geographic inaccessibility
- 32) Refused or unable to obtain consent

** Women of child-bearing potential will be asked to have a baseline pregnancy test done. She must agree to ongoing pregnancy testing during the study, and after end of study therapy. This applies even if the subject practices true abstinence from heterosexual contact. She must either commit to true abstinence from heterosexual contact (which must be reviewed at subsequent study visits and source documented) or agree to use and be able to comply with highly effective

contraception without interruption, during the study therapy (including dose interruptions), and for 30 days after discontinuation of study therapy.

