4.5 WHAT ARE THE MEASURED OUTCOMES FOR THE PILOT STUDY?

The primary feasibility outcome for the pilot study is the number of participants recruited per centre per month. We will obtain baseline details of the patient's type, location and treatment of cancer, and medications. Secondary feasibility outcomes of the pilot study will include, consent rates, loss to follow up, adherence to therapy defining 80% or greater medication taken as having good adherence to study drug, proportion of screened patients who meet eligibility criteria. We will document reasons for non-consent in order to assist recruitment for the larger multicentre trial.

For the full multicentre trial the outcomes would be as follows: primary outcome of symptomatic, radiographically confirmed VTE. Secondary outcomes include major and CRNMB, CVC life span, premature CVC removal, CVC lumen occlusion, CVC associated infection and death.

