4.7 RANDOMIZATION

Consenting subjects will be randomized at 1:1 ratio to treatment or non-treatment arms at study enrollment with treatment allocation determined by central web-based randomization. Randomization will be stratified by gender and the type of central venous catheter (Peripherally Inserted Central Catheter or Hickman/Port-a-Cath/Central line).

Participants will be randomized once the participant has consented and all eligibility criteria have been confirmed.

Randomization will be conducted using a customized web-based program developed for this study. The randomization process will be initiated by the local study coordinator who will access

the web-based system and enter the patient's unique identifier and confirmation of eligibility and informed consent. Specific patient allocation will then be electronically delivered, to the research pharmacy who will prepare and dispense trial medication.

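### Refusal of consent is itself an exclusion criterion, so as written the consent rate in Protocol 8.1.3 is always 100% and refusals by otherwise eligible patients lower the eligibility rate instead

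*Protocol*

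**What the plan says.** Section 8.1.3 lists the secondary proportions, each with a Wilson 95% interval. The first two are "1) proportion of screened subjects who meet eligibility criteria, 2) proportion of eligible subjects who provide consent". The section closes with "Reasons for non-consent will be collected and analyzed using qualitative thematic analysis".

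Section 4.5 names the same quantities among the outcomes: "Secondary feasibility outcomes of the pilot study will include, consent rates, loss to follow up", followed later in that sentence by the share of screened patients who are eligible. It adds: "We will document reasons for non-consent in order to assist recruitment for the larger multicentre trial". The Synopsis repeats both statements under the pilot endpoints.

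The last exclusion criterion in Section 4.4 (item 32) is "Refused or unable to obtain consent". The Synopsis carries the same criterion as item 16. Nothing in the protocol says that the word eligible in 8.1.3 leaves this item out.

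**The concern.** The two proportions are meant to separate two different obstacles to recruitment: too few screened patients qualify, or too few qualifying patients agree. The remedies differ. The first points to the criteria, the second to how the trial is offered. Section 3.4 gives patients' possible unwillingness to take on an extra drug and its bleeding risk as the reason for running a pilot at all, and the consent rate is the outcome that bears on this most directly.

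With refusal inside the exclusion list, the stated definitions do not separate the two. A site that codes a refuser under item 16/32 as excluded takes that patient out of the consent denominator and out of the eligibility numerator. Unwillingness then appears as ineligibility. If the three centres code differently, the pooled rates mix two definitions.

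**Working it through.** **Inputs.** The two definitions and the Wilson method come from 8.1.3, the consent item from 4.4 and the Synopsis, and the target of 100 enrolments from 8.2. The protocol states no expected consent rate, eligibility rate or number screened, so there is no planned figure to reproduce. Those values are assumed below and varied.

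**Notation.** S = screened; E = meeting every criterion other than the consent item; C = those of E who consent.

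| | Intended | As written |
|---|---|---|
| Who is eligible | E | C |
| Consent rate | C/E | C/C = 1 |
| Eligibility rate | E/S | C/S = (E/S) × (C/E) |

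The right-hand column needs no assumed count. The consent rate is fixed at 100%, and the ratio of written to intended eligibility is C/E. Each refusal by an otherwise eligible patient lowers the written eligibility rate by 1/S.

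**Illustration.** C = 100 (8.2), S = 400 (assumed). The Wilson 95% interval has centre (p + z²/2n)/(1 + z²/n) and half-width z√(p(1−p)/n + z²/4n²)/(1 + z²/n), with z = 1.96.

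| E (assumed) | Intended consent C/E | Intended eligibility E/S |
|---|---|---|
| 125 | 100/125 = 80.0% (72.1 to 86.1) | 125/400 = 31.3% (26.9 to 36.0) |
| 200 | 100/200 = 50.0% (43.1 to 56.9) | 200/400 = 50.0% (45.1 to 54.9) |
| 333 | 100/333 = 30.0% (25.4 to 35.2) | 333/400 = 83.3% (79.3 to 86.6) |

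As written, all three rows report the same pair: consent 100/100 = 100% (96.3 to 100) and eligibility 100/400 = 25.0% (21.0 to 29.5).

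**Other screening total.** With S = 600 (assumed), written eligibility is 100/600 = 16.7%, against intended 125/600 = 20.8%, 200/600 = 33.3% and 333/600 = 55.5%. The ratios are again 0.80, 0.50 and 0.30, so the relative understatement does not depend on S.

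**Mixed coding.** Take E = 200 and S = 400, so 100 patients decline, and suppose half of them are coded as excluded (assumed). Reported consent is 100/(100 + 50) = 66.7% instead of 50%, and reported eligibility is 150/400 = 37.5% instead of 50%. Partial use of item 16/32 therefore shifts both rates, and the result looks plausible in a way that 100% would not.

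**Consistency with the rest of the protocol.** A consent rate that cannot differ from 100% is not an outcome worth listing, and an analysis of reasons for non-consent presupposes refusals. The conflict is therefore between the exclusion item and 8.1.3, 4.5 and the Synopsis endpoints.

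**The case against.** The strongest reply is that the intent is obvious. Within 8.1.3 itself, the literal reading would make one listed analysis a constant while the same paragraph plans to study why people refuse. Few analysts would report consenters over consenters. Denominator details and log categories are also often left to a SAP or a study manual, and no SAP is at hand. Much of this stands, and it is why the point is minor. It does not remove the conflict: the criteria and both definitions are fixed in the protocol, and together they give a result its authors did not want. Clear intent shows which way to correct the text.

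Four stronger readings are tempting and are not supported.

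- *Every refusal lowers the eligibility rate.* Only refusals by patients who meet all other criteria do. A refuser who already fails another criterion changes nothing.
- *The consent rate cannot be obtained from this pilot.* Refusers have to be identified anyway, because their reasons are collected. If their other criteria are logged too, C/E can be calculated. Section 6.1 has one coordinator train and monitor the centres, and 8.1.1 foresees data on excluded subjects, so consistent logging is within reach.
- *The enrolment wording contradicts the exclusion item.* The Synopsis ("Consenting participants, meeting eligibility criteria will be randomized at the time of enrollment"), Section 4.3 ("Eligible and consenting patients") and Section 4.7 ("Participants will be randomized once the participant has consented and all eligibility criteria have been confirmed") name consent and eligibility as two conditions. If consent is also a criterion, these phrases are redundant, not contradictory.
- *The feasibility decision is compromised.* The primary outcome is recruitment per centre per month, which does not use either proportion, and the protocol sets no threshold for consent or eligibility.

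**Conclusion.** The point holds as a minor defect of definition. Applied as written, 8.1.3 with the exclusion lists gives a consent rate of 100% by construction and an eligibility rate equal to intended eligibility times consent. That result is algebraic and rests on no assumption. The size of the distortion does: eligibility is understated by 20%, 50% or 70% at assumed consent of 80%, 50% or 30%. These figures show what the written rule would do, not what the sites are likely to report.

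Two secondary, descriptive feasibility outcomes are affected. The primary recruitment rate, randomization, treatment and sample size are not. The practical risk is that some refusers are coded under item 16/32 and leave the consent denominator.

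**What to change.** In 8.1.3, define eligible as meeting the inclusion criterion and none of the exclusions other than the consent item, that is items 1 to 15 in the Synopsis and 17 to 31 in 4.4. Removing the consent item from both exclusion lists would do the same.

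In the screening log, split otherwise eligible non-participants into two groups: declined (D), and unable to obtain consent or not approached (U). Then E = C + D + U, the eligibility rate is E/S, the consent rate is C/(C + D), and U is reported as its own count. The split is needed because taking out the whole item would otherwise put patients who were never able to answer into the consent denominator, lowering the rate for reasons unrelated to willingness.

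The cost is one clause in 8.1.3 (or one deletion in each list) and a matching line in the log instructions. It is best settled before screening starts, since a refuser logged only as excluded may be hard to reclassify later.

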4.2 TRIAL DESIGN

TRIM-Line is an open-label, randomized controlled feasibility pilot trial comparing rivaroxaban 10mg po daily vs standard of care (no treatment) in patients with active cancer and indwelling CVC. This will involve 3 centres, Ottawa as the coordinating centre, Halifax and Edmonton.

Cancer patients with insertion of CVC will be eligible.

While the primary outcome is feasibility based clinical data will be collected using the same methodology as the proposed full-sized trial. Should there be no major changes to the trial design based on the findings of this pilot study's feasibility data that would render the collected data inappropriate for inclusion, the clinical data collected during this trial will be included in the primary and secondary analysis for the full trial.

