8.2 DETERMINATION OF SAMPLE SIZE

Using an alpha=0.05, 80% power and event rate estimates of 6.8% in the untreated and 3.7% in the treated population, the estimated sample size would be 860 patients per arm or 1720 patients in total for the full trial. Estimating a 10% lost to follow up this would lead to a required sample of 1892 patients. Enrollment data, event rates, and study drop out will be assessed in this pilot trial will aid in the calculation of the required sample size for the full trial. Due to the low event rates, small differences in the event rates in either patient population will lead to large changes in the sample size required.

For the purposes of the pilot the target sample size is 100 patients with plans to run the pilot trial for 1 year. This would involve 4-6 enrollments/month at the coordinating centre in Ottawa, and 2 enrollments per month at the sites of Halifax and Edmonton.

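### Section 8.1.3 reduces start-up time at three sites to a proportion above 18 months, whose 95% interval is at least 56 points wide whatever the result

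*Protocol*

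**What the plan says.** Protocol section 8.1.3 opens its list of secondary analyses with "Proportions with 95% confidence intervals will be calculated using Wilson's score method for the following secondary analyses". Item 4 of that list is the "proportion of sites requiring >18 months to obtain all required approvals/contracts from time of delivery of all study documents". The clock therefore starts at document delivery, and the denominator is the number of sites.

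Section 4.2 fixes that number: "This will involve 3 centres, Ottawa as the coordinating centre, Halifax and Edmonton".

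The length of the pilot is given in two ways. The synopsis has "Timeline: February 2019-September2019", which is 8 calendar months. Section 8.2 says "the target sample size is 100 patients with plans to run the pilot trial for 1 year", and plans "4-6 enrollments/month at the coordinating centre in Ottawa, and 2 enrollments per month at the sites of Halifax and Edmonton".

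The protocol gives no date for document delivery, no data cut-off for this outcome and no reason for choosing 18 months. The nearest date is "Protocol Version: 28Feb2018 Version 1.1" in the synopsis. Section 4.5 lists the secondary feasibility outcomes ("Secondary feasibility outcomes of the pilot study will include, consent rates, loss to follow up, adherence to therapy", then the proportion of screened patients who are eligible), and start-up time is not among them. It appears only in section 8.1.3.

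**The concern.** The pilot is meant to show whether a multicentre trial of 1892 patients can be launched, and the time sites need to open bears on that. Item 4 takes one duration per site, keeps only whether it exceeds 18 months, and then treats three yes/no answers as a sample from which to estimate a proportion.

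Two things are lost. First, three sites cannot estimate a proportion with useful precision, and one of the three is the coordinating centre, which may not represent an ordinary joining site. Second, the cut-off does not separate a site that opens in 3 months from one that opens in 17, although that difference matters to a pilot of 8 or 12 months. A result of 0/3 could be reported when every site had taken more than a year to open.

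**Working it through.** **Inputs.** Number of sites: 3 (section 4.2). Interval: Wilson score, 95% (section 8.1.3). Cut-off: more than 18 months from document delivery (section 8.1.3). Pilot length: 8 months (synopsis) or 12 months (section 8.2). Planned accrual: 4 to 6 per month in Ottawa, and 2 per month at each of Halifax and Edmonton (section 8.2).

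**The plan's own figure.** (4 to 6 + 2 + 2) × 12 = 96 to 120, which contains the target of 100. Reading the 2 per month as applying to each site is what makes this work. Over 8 months the same rates give 64 to 80.

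**Precision with three sites.** The Wilson limits are centre ± half-width, with

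- centre = (p + z²/2n) / (1 + z²/n)
- half-width = z √(p(1−p)/n + z²/4n²) / (1 + z²/n)

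With z = 1.96 and n = 3: z²/2n = 0.640, z²/4n² = 0.1067 and 1 + z²/n = 2.2805.

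- 0/3: 0.281 ± 0.281, or 0 to 56.2% (width 56 points)
- 1/3: 0.427 ± 0.365, or 6.1 to 79.2% (width 73 points)
- 2/3: 0.573 ± 0.365, or 20.8 to 93.8% (width 73 points)
- 3/3: 0.719 ± 0.281, or 43.8 to 100% (width 56 points)

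These four are the only possible results. If the true share of slow sites is p, the chance of seeing 0/3 is (1 − p)³: 51% at p = 0.20, 34% at p = 0.30 and 12.5% at p = 0.50. Without the coordinating centre, 0/2 gives 0 to 65.8%.

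**What the cut-off lets through.** This part rests on assumptions. Take a common calendar window starting on 1 February 2019 and ending on 30 September 2019 (8 months) or 31 January 2020 (12 months). Consider a site planned at 2 per month, that is 16 or 24 patients.

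Delivery on the version date, 28 February 2018:

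- 12 months to open: opens end of February 2019. It keeps 7 of 8 months (14 of 16 patients) or 11 of 12 months (22 of 24).
- 17 months: opens end of July 2019. It keeps 2 of 8 months (4 of 16) or 6 of 12 months (12 of 24).
- Just over 18 months: opens end of August 2019. It keeps 1 of 8 months (2 of 16) or 5 of 12 months (10 of 24).

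Delivery five months later, at the end of July 2018 (an illustrative date):

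- 12 months: opens end of July 2019. It keeps 4 of 16 or 12 of 24 patients.
- 17 months: opens end of December 2019. It keeps 0 of 16 or 2 of 24 patients.

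In both cases the sites at 12 and 17 months count as not slow. Their loss ranges from 2 patients to the whole allocation. The size of the loss depends on a delivery date that the protocol does not give.

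**The case against.** The strongest objection concerns timing. A reader might infer that a cut-off of more than 18 months contradicts a pilot of 8 to 12 months, that no site could be classed as slow, and that the result is therefore as good as fixed at 0/3. The protocol does not support this. The 18 months run from document delivery, while the 8 and 12 months describe when the pilot runs. Section 9.2 requires ethics approval at the other centres before the study is initiated there, so start-up precedes a site's enrolment. If documents went out on the version date, the 18-month mark falls at the end of August 2019, inside even the shorter window. A site still without approval after 18 months counts as slow whether or not it enrols anyone. Section 8.2 does not say whether the year runs from a common start or from each site's activation; in the second case a late site loses no enrolment time. The protocol also gives no distribution of start-up times from which to predict the result. This part of the objection stands.

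It can also be said that 18 months may be a tolerance chosen for the full trial, that a reported interval of 0 to 56% would itself show how little three sites can tell, and that nothing in section 8.1.3 forbids listing each site's time. These are fair and lower the severity. They do not rescue the proportion: its width follows from the denominator of 3 and is the same under any timing.

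**Conclusion.** The point holds on the denominator. With three sites, every possible result of item 4 has a 95% interval at least 56 points wide, and 0/3 leaves a true share of one half within its limits. This needs no assumption beyond the number of sites and the stated method. If anything it flatters the outcome, since the interval treats the coordinating centre as exchangeable with future sites.

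The coarseness of the cut-off is a supporting argument. It assumes a common calendar window, and its size depends on the undated delivery of documents.

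It would go too far to say that the pilot cannot inform the full trial about start-up. The three durations themselves would be informative; it is the dichotomy with its interval that discards them. Severity is minor: this is one of five secondary analyses, is absent from the outcomes listed in section 4.5, and has no progression rule tied to it.

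**What to change.** Replace item 4 of section 8.1.3 with the time in months from delivery of the study documents to full approval and contract, and from delivery to first enrolment. List both for each of the three sites, with median and range, and show the coordinating centre separately. State the delivery date used for each site and the data cut-off, so that a site still waiting can be shown with its elapsed time. If 18 months matters as a tolerance for the full trial, give the count of sites above it descriptively, without a confidence interval. The cut-off need not be moved inside the pilot period, because the two clocks differ.

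The cost is about one sentence of text. The approval dates are already needed for the current outcome, and the trial will hold the first-enrolment dates. What is given up is a proportion and an interval that carry almost no information.
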